1. AMENDMENTS FROM PREVIOUS VERSION(S)

Version	Date	Author(s)	Summary of Changes/Comments
2.1	May 09, 2017	PPD	
 Section 5.1 excluded subjects from site 1015 (a total of 4 subjects) from FAS
2.0	May 02, 2017	PPD	
 Section 3 interim analysis re-written to clarify goals and time of IA Section 7.1 re-written to clarify the missing value imputation proposal on efficacy data Section 8.1.1 removed summary statistics for NR and LOCF imputation. Summary stats will only be generated for FAS with OC except a few key efficacy endpoints Section 8.1.1.1 removed sensitivity analyses using GLMM on FAS with NR and LOCF. Logistic regression with NR imputation will be performed regardless of GLMM convergence Section 8.1.1.3 changed Santner and Snell method to Chan and Zhang method Section 8.1.2 added ANCOVA analysis for percent change from baseline in EASI with LOCF imputation Section 8.1.3 added statistical methods for time-to-event variables Section 8.2.2.1 removed sensitivity analyses using GLMM on FAS with NR and LOCF Section 8.2.2.2.1 clarified that sensitivity analysis will be performed using ANCOVA on FAS with LOCF imputation Section 8.2.2.2.2 changed logistic regression analysis at each time point with LOCF imputation to NR imputation Section 6.1.2.3 added four more secondary endpoints: 1) proportion of subjects achieving ≥ 4 points improvement in the pruritus numerical rating scale (NRS) from baseline at all scheduled time points 2) Percent change from baseline in SCORing atopic dermatitis (SCORAD) at all scheduled time points 3) Time to achieving ≥ 3 points improvement in NRS 4) Time to achieving ≥ 4 points improvement in NRS Section 8.2.2.2.2 added survival analysis for time to NRS response Section 8.2.2.2.2 added: “For endpoint “Proportion of subjects achieving ≥ 3

090177e18dabc776\0.1\Draft\Versioned On:07-Feb-2018 10:11 (GMT)

			
points improvement in the pruritus numerical rating scale (NRS) from baseline at all scheduled time points”, subjects with baseline NRS ≤ 2 will be considered as non-responders.” And “For endpoint “Proportion of subjects achieving ≥ 4 points improvement in the pruritus numerical rating scale (NRS) from baseline at all scheduled time points”, only subjects with baseline NRS ≥ 4 will be analyzed”.
 
 • Section 8.2.2.4 sensitivity analysis was removed • Section 8.2.3 Santner and Snell changed to Chan and Zhang method • Section 8.2.5 summary table of statistical analysis updated
1.0	March 09, 2016	PPD	First version

2. INTRODUCTION

Note: in this document any text taken directly from the protocol is *italicised*.

This study B7451006 is a phase 2b POC study which is planned to assess four PF-04965842 once daily (QD) doses (10, 30, 100, 200 mg) relative to placebo over 12 weeks to characterize the efficacy and safety of PF-04965842 in subjects with moderate to severe Atopic Dermatitis AD. The objectives of the study are to demonstrate the efficacy of PF-04965842 by showing improvement in disease severity in patients with moderate to severe AD as measured by the Investigator's Global Assessment (IGA) and Eczema Area and Severity Index (EASI) scores, and safety to support further clinical development of PF-04965842.

Complete information for this compound may be found in the single reference safety document (SRSD), which for this study is the Investigator's Brochure (IB).

2.1. Study Design

[figure not shown]
This Phase 2b, multi-center, randomized, double-blind, 5-arm, parallel group study will enroll a total of approximately 250 subjects (providing approximately 200 completers, 40 subjects per treatment group). The study will be conducted at approximately 60 sites.

Subjects who have chronic AD that has been present for at least 1 year (prior to screening visit) and affected BSA of $\geq 10\%$, EASI ≥ 12 and IGA ≥ 3 at the screening and baseline visits will be included in the study. Subjects must also have a documented history of inadequate response to treatment with topical medications given for at least 4 weeks, or for whom topical treatments are otherwise medically inadvisable (eg, because of important side effects or safety risks) within 12 months of the first dose of study drug. Subjects will be randomized to 1 of 4 treatment groups or placebo in the ratio of 1:1:1:1. Investigators, subjects, and the sponsor study team will be blinded as to treatment group.

Subjects will be screened within 35 days prior to the first dose of study drug to confirm that they meet the subject selection criteria for the study. There will be a 12-week double-blind treatment period as well as a 4-week follow up period.

An interim analysis may be performed when approximately a total of 110 randomized subjects complete 6 weeks of study or discontinue prematurely from study in order to assess the percent change of EASI score from baseline as well as other safety and efficacy endpoints such as IGA response as appropriate.

Figure 1. Study Design Schematic

2.2. Study Objectives

2.2.1. Primary Objective

- *The primary objective of this study is to evaluate the efficacy of 4 QD dose levels (10, 30, 100, and 200 mg) of PF-04965842 relative to placebo in adult subjects with moderate to severe atopic dermatitis, using the Investigator's Global Assessment (IGA).*

2.2.2. Secondary Objectives

- *To evaluate the effect of PF-0465842 on additional efficacy endpoints and patient reported outcomes over time in adult subjects with moderate to severe atopic dermatitis.*
- *To evaluate the safety and tolerability of PF-0465842 over time in adult subjects with moderate to severe atopic dermatitis.*

2.2.3. CCI [REDACTED]

- CCI [REDACTED]
- [REDACTED]

3. INTERIM ANALYSES, FINAL ANALYSES AND UNBLINDING

An interim analysis (IA) will be performed when approximately 50% subjects complete 6 weeks of study or discontinue prematurely from study in order to assess the percent change of EASI score from baseline (primary endpoint for IA) as well as other efficacy and safety endpoints such as IGA response, itch response measured by Pruritus Numeric Rating Scale (NRS) and hematological parameters as appropriate. *The study team and investigators will*

090177e18dabc776\0.1\Draft\Versioned On:07-Feb-2018 10:11 (GMT)

remain blinded to the results of the interim analysis. It is expected that all interim analysis data from the treatment phase of the study will be as clean as possible and that all clinical relevant queries will have been addressed. Access to the database containing individual treatment group assignments will be restricted to the unblinded support team including programmer, statistician, clinician and clinical pharmacologist. Paper copies of the treatment assignments will not be kept and any copies printed for temporary checks of the data will be destroyed.

Interim analysis results will be used for internal business decision regarding future study planning. The results will have no impact on the ongoing study. Additional logistical details will also be provided in the Internal Review Committee (IRC) Charter.

4. HYPOTHESES AND DECISION RULES

4.1. Statistical Hypotheses

Statistical inference will be made on the primary endpoint: Proportion of subjects achieving the IGA for clear (0) or almost clear (1) and ≥ 2 points improvement from baseline at Week 12. The null hypothesis is that there is no difference between any dose of PF-04965842 (200mg, 100mg, 30mg and 10mg) and placebo on the primary endpoint. The alternative hypothesis is that at least one dose of PF-04965842 is superior to placebo on the primary endpoint.

4.2. Decision Rules

4.2.1. Dose Response Modeling

A three-parameter Emax model will be employed for dose-response fitting for the primary endpoint (IGA response at Week 12). If a monotonic dose-response curve is detected, then model estimates and the corresponding treatment effect along with 95% confidence intervals will be reported.

If the data do not support an Emax model, the decision rule may be based on pairwise comparison analysis.

4.2.2. Multiplicity Adjustment

The multiplicity adjustments are considered only in the analysis of the primary endpoint when the Emax model does not fit. Hochberg method (Hochberg, 1988) is used to account for that the null hypothesis will be rejected if a treatment effect is detected at Week 12. The overall Type I family-wise error rate (FWER) is controlled at 0.05 (one-sided).

4.2.3. Decision Rules for the Interim Analysis

This study will not stop irrespective of whether statistical significance has been reached at the interim analysis for any efficacy endpoint. However the results from interim analysis may be used for internal planning purpose.

4.2.4. Efficacy Analysis and Sample Size Justification

The sample size is based on the primary efficacy endpoint, IGA response rate of clear or almost clear and ≥ 2 points improvement at Week 12. For IGA response rate at Week 12, a total of 250 randomized subjects in the 5 treatment groups (providing approximately 200 completers, 40 completers per treatment group assuming 20% dropout rate) will provide approximately 95% power to detect a 33% difference between PF-04965842 and placebo assuming placebo response rate is approximately 10%, and significance level is 0.0125 (Bonferroni adjusted with 4 comparisons).

5. ANALYSIS SETS

5.1. Full Analysis Set

As specified in the protocol, the analysis of the efficacy, health outcome and biomarker endpoints will be performed for the modified intent-to-treat (mITT) population, defined as all randomized subjects who receive at least 1 dose of investigational product. This population is also called as the Full Analysis Set (FAS). All subjects from site 1015 (total = 4 subjects) will be excluded from FAS due to major protocol deviations.

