9. DATA ANALYSIS/STATISTICAL METHODS

This section outlines the key planned statistical summaries and analyses for the data collected in this study. A comprehensive overall Statistical Analysis Plan (SAP) will be provided prior to the un-blinding of the trial. The SAP may modify the plans outlined in the protocol; however, any major modifications of planned analyses will be reflected in a protocol amendment if it is modified before data un-blinding. If, after the trial is un-blinded, changes are made to the SAP, then these deviations to the plan will be documented, along with an explanation as to why they occurred, in the Clinical Study Report (CSR).

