9.2. Efficacy Analysis

9.2.1. Analysis of the Primary Endpoint

When the 12 week treatment period is completed, the analysis of the primary endpoint will be conducted. The primary endpoint is the proportion of IGA responders at Week 12 and the corresponding primary analysis will be based on the normal approximation for the difference in binomial proportions (such as IGA response rates) to test the superiority of each dose of PF-04965842 to placebo at Week 12. Subjects who receive at least one investigational product and discontinue from the study before Week 12 will be considered as non-responders for the primary endpoint (IGA) for all subsequent visits during the treatment phase until Week 12. Bayesian analysis using a non-informative prior (such as Jeffery's prior) may be employed if the normality assumption does not hold.

Sensitivity analysis will be performed with a generalized linear mixed model utilizing the data from all scheduled visits if there is no convergence issue. This model will have fixed effects for time, treatment, time by treatment interaction and other potential covariates. The dependent variable will be logit of the probability of “response”. An unstructured correlation may be used to model the association between observations within a subject. The modified intention-to-treat (mITT) population will be the subjects who receive at least one dose of randomized investigational product (PF-04965842 or placebo). In addition, dose-response analysis using an Emax model may be provided for the primary endpoint.

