5.5.2. Deviations Assessed Post-Randomization

Post-randomization deviations include:

- Subjects who receive excluded concomitant medications or rescue medications during the treatment period as described in Section 5.8 of the Protocol;
- Subjects who were randomized but took incorrect treatment;
- Subjects not satisfying the eligibility criteria, although, not identified until after randomization occurred.

Any significant deviation or violations from the protocol will be reviewed by the clinical team during the course of the study and prior to database closure and a decision taken regarding evaluation for each analysis set.

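### SAP 5.1 equates the FAS with the protocol's mITT population but removes site 1015's four subjects, and no efficacy analysis uses the full mITT set

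*SAP*

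**What the plan says.** Protocol 9.2.1 defines the efficacy population by dosing alone: "The modified intention-to-treat (mITT) population will be the subjects who receive at least one dose of randomized investigational product". It makes no exception for a site or for deviations.

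SAP 5.1 says it follows the protocol and describes the mITT population, which it also calls the FAS, as "defined as all randomized subjects who receive at least 1 dose of investigational product". The same paragraph ends: "All subjects from site 1015 (total = 4 subjects) will be excluded from FAS due to major protocol deviations". The deviations are not described. The SAP's version history dates this sentence to version 2.1, one week after version 2.0.

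SAP 8.2.2 bases efficacy, health-outcome and biomarker analyses on the FAS unless stated otherwise. The sensitivity analyses in 8.1.1.1, 8.2.2.1, 8.2.2.2.1 and 8.2.5 are a generalised linear mixed model on observed cases, logistic regression with non-responder (NR) imputation, ANCOVA with last observation carried forward, and a repeated-measures model for absolute EASI change. None uses a wider population.

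The four are not lost from every report. The safety set (5.2) is all dosed subjects, the PK set (5.3) is drawn from the safety set, and demography (8.2.1) covers all randomised and treated subjects.

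**The concern.** The label and the content of the FAS disagree. A reader who takes 5.1 at its word will believe that the primary result rests on the protocol's mITT population, when that population is never analysed for efficacy. Because the deviations are unnamed, the reader cannot judge whether the data were unusable or merely imperfect. Because no inclusive analysis is planned, the reader cannot see whether the choice mattered.

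The SAP also handles another kind of major deviation the opposite way. Under 5.4, subjects who took the wrong treatment stay in their randomised group for efficacy, and if the errors amount to a major deviation, their exclusion is at most a sensitivity analysis. For site 1015 exclusion is the primary approach and there is no inclusive counterpart. The SAP gives no reason for the difference.

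**Working it through.** **Inputs.** 250 randomised in five equal arms, so 50 per arm; placebo rate 10%; difference 33 points, so 43% on active; significance level 0.0125 (SAP 4.2.4, Protocol 9.1). Four subjects removed (SAP 5.1). I assume that all four were randomised and dosed. Their arms and outcomes are not given, so everything below is a range, not an estimate.

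**Planned power.** For two proportions with pooled variance under the null, power = Φ{[(p1 − p0) − z·√(p̄(1 − p̄)(1/n0 + 1/n1))] / √(p0(1 − p0)/n0 + p1(1 − p1)/n1)}. With 50 per arm and one-sided 0.0125 (z = 2.241) this gives 94.7%, which reproduces the stated 95%.

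**Power after the exclusion, same basis.**

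| Removal | Power |
|---|---|
| none | 94.7% |
| spread evenly (49.2 per arm) | 94.3% |
| all four from one active arm (46 v 50) | 93.8% |
| all four from placebo (50 v 46) | 93.6% |

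The largest loss is 94.68 − 93.63 = 1.05 points. With 40 completers per arm the worst case is larger (88.3% to 86.0% one-sided, 81.9% to 78.8% two-sided). That basis does not reproduce 95%, and this worst case needs four completers all from placebo.

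**Share removed.** 4/250 = 1.6%.

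**Movement of one arm's rate.** Take an active arm at 22/50 = 44.0% and placebo at 5/50 = 10.0%. If k of the four were in that arm, the rate becomes (x − k)/(50 − k) when they were responders and x/(50 − k) when they were not.

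| k | Active, responders / non-responders removed | Placebo, responders / non-responders removed |
|---|---|---|
| 1 | 21/49 = 42.9% / 22/49 = 44.9% | 4/49 = 8.2% / 5/49 = 10.2% |
| 2 | 20/48 = 41.7% / 22/48 = 45.8% | 3/48 = 6.3% / 5/48 = 10.4% |
| 4 | 18/46 = 39.1% / 22/46 = 47.8% | 1/46 = 2.2% / 5/46 = 10.9% |

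The largest shift is 1.8 points for k = 1 and 3.8 points for k = 2.

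**How likely each pattern is.** Assuming independent, equal allocation, no arm has more than one of the four with probability (5·4·3·2)/5⁴ = 19.2%; the fullest arm has three with probability 5·4·(1/5)³·(4/5) = 12.8%, and four with 5·(1/5)⁴ = 0.8%; so it has two with 67.2%. The large placebo shifts also need the removed patients to be responders, which is uncommon at a 10% rate.

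**Can a comparison change?** Illustration with the normal-approximation test of Protocol 9.2.1 and one-sided 0.0125:

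- Full set, 13/50 v 5/50: z = 2.08, p = 0.019.
- Four active non-responders removed, 13/46 v 5/50: z = 2.29, p = 0.011.
- One active non-responder and one placebo responder removed, 13/49 v 4/49: z = 2.40, p = 0.008.
- One non-responder removed from each arm, 13/49 v 5/49: z = 2.09, p = 0.018, so no change.

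A crossing is possible with as few as two subjects, but only when the result is already near the threshold.

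**The case against.** The strongest reply is that removing a whole named site for unreliable data is legitimate. It takes out patients regardless of arm or response, so the remaining sites still form a randomised comparison unless the site was picked with knowledge of treatment or outcome. The documents do not suggest that: Protocol 5.2 keeps the study team blinded and SAP 3 keeps it blinded to interim results, although the SAP does not state the blinding of this particular decision. The exclusion is disclosed, with site and count fixed in the text. This stands, and it is why the exclusion itself is not the fault.

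The primary SAP analysis is an Emax model across all arms, so single-arm rates are not the primary estimate. That also stands and makes a visible effect less likely.

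The amendment rule is weaker than it looks. Protocol 9 lets the SAP modify the plan and says only that "any major modifications of planned analyses will be reflected in a protocol amendment if it is modified before data un-blinding". Whether removing 1.6% of subjects is major is a judgement, so a breach cannot be asserted.

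A reader might also infer that SAP 5.5.2 drops patients found ineligible after randomisation. It lists them as deviations and provides for review "prior to database closure and a decision taken regarding evaluation for each analysis set". That permits an exclusion but does not order one.

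**Conclusion.** The point holds as a cheap improvement. SAP 5.1 calls a reduced set the protocol population, and no planned efficacy analysis uses the population that Protocol 9.2.1 defines. The expected effect is small: 1.6% of subjects, about 1 point of power at most on the basis that reproduces 95%, and single-arm shifts of at most about 2 points with one removed per arm or about 4 with two. These figures assume 50 per arm and the planning rates; the chances of each pattern also assume independent equal allocation.

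Three stronger readings are tempting and not supported. The four are not absent from all analyses: they stay in safety, in demography, and in PK if sampled. The difference between efficacy and safety sets is not a defect, since SAP 5.4 already puts subjects treated without randomisation in one and not the other. Nor do the documents show that the inclusive set must be primary; with the deviations undescribed, nobody outside the sponsor can say whether the site's data are usable.

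**What to change.** Keep the site 1015 exclusion for the primary analyses if the sponsor judges the data unreliable, and make two changes.

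1. In SAP 8.2.2 and the table in 8.2.5, add a sensitivity analysis on the full protocol mITT set, including site 1015, for the primary endpoint (Emax model, NR imputation) and the key secondary endpoint (repeated-measures model for percent change in EASI at Week 12).
2. In SAP 5.1, define the protocol mITT population first, then define the FAS as that population without site 1015, so that the two are no longer called the same. A clause naming the deviations would let a reader judge the reason.

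The cost is a few sentences and two reruns of code that already exists. The downside is that four patients with questionable data enter one reported sensitivity analysis, which its label makes plain.

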5.2. Safety Analysis Set

The safety analysis set (SAS) will be all subjects who receive at least 1 dose of investigational product. The safety analysis set will include the follow-up period. The safety analysis set excluding follow-up period data may be conducted as a sensitivity analysis.

The final safety database will include all reported safety data at the time of database release.

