2.4.2.2. Safety Endpoints

- Incidence of treatment-emergent adverse events.
- Incidence of specific clinical laboratory abnormalities (anemia, neutropenia, thrombocytopenia, lymphopenia, lipid profile, liver function tests [LFTs]).

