8.2. Reporting Period

For SAEs, the active reporting period to Pfizer or its designated representative begins from the time that the subject provides informed consent, which is obtained prior to the subject's participation in the study, ie, prior to undergoing any study-related procedure and/or receiving investigational product, through and including 28 calendar days after the last administration of the investigational product. SAEs occurring to a subject after the active reporting period has ended should be reported to the sponsor if the investigator becomes aware of them; at a minimum, all SAEs that the investigator believes have at least a reasonable possibility of being related to investigational product are to be reported to the sponsor.

AEs (serious and non-serious) should be recorded on the case report form (CRF) from the time the subject has taken at least 1 dose of investigational product through the subject's last visit.

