8.3. Definition of an Adverse Event

An AE is any untoward medical occurrence in a clinical investigation subject administered a product or medical device; the event need not necessarily have a causal relationship with the treatment or usage. Examples of AEs include but are not limited to:

- Abnormal test findings;
- Clinically significant symptoms and signs;
- Changes in physical examination findings;
- Hypersensitivity;
- Progression/worsening of underlying disease;
- Drug abuse;
- Drug dependency.

Additionally, they may include the signs or symptoms resulting from:

- Drug overdose;
- Drug withdrawal;
- Drug misuse;
- Drug interactions;
- Extravasation;
- Exposure during pregnancy (EDP);
- Exposure via breastfeeding;
- Medication error;
- Occupational exposure.

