9.3. Safety Analysis

All subjects who receive investigational product (safety population) will be included in the safety analyses. All the safety data will be summarized descriptively through appropriate data tabulations, descriptive statistics, categorical summaries, and graphical presentations. Safety endpoints for the study include:

- On-treatment AEs and SAEs.
- Withdrawals from active treatment due to AEs.
- Serious infections, defined as any infection (viral, bacterial, and fungal) requiring hospitalization or parenteral antimicrobials.
- Safety laboratory tests (eg, anemia, neutropenia, thrombocytopenia, lymphopenia, lipid profile, LFTs).
- Vital signs.

- ECG parameters if applicable.

Safety data will be reviewed and summarized on an ongoing basis during the study to evaluate the safety of subjects. A set of safety summary tables by treatment will be produced to evaluate any potential risk associated with the safety and toleration of administering the investigational product, continuous outcomes (eg, blood pressure, heart rate etc.) will be summarized using N, Mean, Median, Standard Deviation etc. Categorical outcomes (eg, occurrence of any adverse event) will be summarized by subject counts and percentage. Change from baseline on laboratory data and vital signs will be additionally summarized. Subject listings will also be produced for these safety endpoints. The safety endpoints will be listed and summarized in accordance with Pfizer Data Standards. The safety analyses will be carried out in the safety population, detailed analyses will be described in the SAP.

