6.1.2.4. Safety Endpoints

- *Incidence of treatment emergent adverse events.*
- *Incidence of specific clinical laboratory abnormalities (anemia, neutropenia, thrombocytopenia, lymphopenia, lipid profile, liver function tests [LFTs]).*

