7.4. Safety Endpoints

Missing data for safety endpoints will not be imputed and will be left as missing. The follow-up period will be included for the safety endpoint. A sensitivity analysis maybe carried out excluding the follow-up period.

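### The SAP's guaranteed adverse-event comparisons pool on-drug and off-drug events; an on-treatment version is only optional, and no AE window is defined

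*SAP*

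**What the plan says.** The protocol uses two terms for the AE endpoint. The endpoint list in 2.4.2.2 has "Incidence of treatment-emergent adverse events". Protocol 9.2.3 uses the same term, and SAP 6.1.2.4 carries it over as "Incidence of treatment emergent adverse events". The safety-analysis section, Protocol 9.3, instead lists "On-treatment AEs and SAEs", as does the protocol summary. Neither term is given a start and end.

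Collection runs beyond dosing. Protocol 8.2 records AEs from the time the subject has "taken at least 1 dose of investigational product through the subject's last visit". The active reporting period for SAEs runs "through and including 28 calendar days after the last administration of the investigational product".

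The SAP sets the analysis window. Section 5.2: "The safety analysis set will include the follow-up period". Section 7.4: "The follow-up period will be included for the safety endpoint". In both places the version without follow-up is a sensitivity analysis that may be done. SAP 8.2.3 takes its population from 5.2 and compares each dose with placebo on tier 1 and tier 2 AEs, using risk differences with 90% confidence intervals. SAP 8.1.1.3 and 8.2.3 add exposure-adjusted summaries for the same tiers.

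Protocol 8.3 gives "Progression/worsening of underlying disease" as an example of an AE.

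**The concern.** Dosing runs from Day 1 to Day 85, and follow-up runs to about Day 113. The protocol reports a mean terminal half-life of 2.8 to 5.0 hours on repeat dosing (Protocol 1.5), so nearly all of the follow-up is off drug.

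Pooling the two periods can act on a dose-versus-placebo contrast in two ways:

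- **Flares.** If an effective dose is stopped and the dermatitis returns, the worsening can be recorded as an AE and counted against that dose. Placebo subjects have no drug effect to lose.
- **Background events.** Events that arise at the same rate in every arm off drug dilute a real on-drug excess.

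These push in opposite directions, so the net effect cannot be recovered from the pooled table alone. In a dose-ranging trial the by-dose AE contrast informs later dose choice. As written, no on-treatment contrast is guaranteed, although Protocol 9.3 lists one.

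**Working it through.** The plan states no figure on this point, so there is none to reproduce. Day counts come from the documents; **every event rate and hazard ratio below is an assumption**.

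**1. Time in each period (completer).** On-drug days: 85. Follow-up days: 113 − 85 = 28. Follow-up adds 28/85 = 33% to the on-drug time and makes up 28/113 = 24.8% of the total.

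**2. Dilution.** Assume a constant hazard, placebo risk p by Day 85, on-drug hazard ratio HR, and equal hazards off drug.

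- On-treatment difference: (1 − (1−p)^HR) − p.
- Difference through Day 113: (1 − (1−p)^(HR + 28/85)) − (1 − (1−p)^(1 + 28/85)). This equals the on-treatment difference times (1−p)^(28/85).

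| p | HR | On treatment | Through Day 113 |
|---|---|---|---|
| 5% | 2 | 4.75 points | 4.67 points |
| 10% | 2 | 9.0 | 8.7 |
| 30% | 1.5 | 11.4 | 10.2 |
| 50% | 1.3 | 9.4 | 7.5 |

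Tier 2 is defined by preferred term, so the first two rows are the closer guide. The last two look more like any-AE incidence. For scale, with 50 per arm the approximate 90% half-width, 1.645 × √(p₁(1−p₁)/50 + p₂(1−p₂)/50), is 8.6 points for 5% against 9.75% and 11.5 points for 10% against 19%. Dilution of 0.1 to 0.3 points is lost inside that.

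**3. Flares.** Combined risk in an arm = 1 − (1 − on)(1 − off). Take AD-worsening AEs on drug at 12% (placebo) and 4% (effective dose), a difference of −8.0 points. Set the off-drug risk at 2% on placebo and 5, 10 or 15% after the effective dose.

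- Placebo: 1 − 0.88 × 0.98 = 13.8%.
- Effective dose: 1 − 0.96 × 0.95 = 8.8%; 1 − 0.96 × 0.90 = 13.6%; 1 − 0.96 × 0.85 = 18.4%.
- Pooled difference: −5.0, −0.2 or +4.6 points.

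A second set of assumptions starts from 10% on treatment in both arms, with an off-drug risk of 5 to 20% (active) and 0 to 5% (placebo). A true on-treatment difference of 0 then becomes 0 to 18 points.

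**4. Entry to tier 2.** The threshold is at least 4 in any group. With 50 per arm, an on-treatment incidence of 3 to 5% gives one arm a 6 to 24% chance of reaching 4. If a further 3 to 10% have the event in follow-up, the chance is 34 to 94%. These follow-up rates suit a flare-type term. A term at 3% over 85 days with constant hazard would add only about 1 − 0.97^(28/85) = 1.0%.

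**5. Exposure.** SAP 8.2.1 defines exposure as days known to be on study drug, but computes it as last visit (follow-up included) minus first dose plus one. A completer gets 113 days, not 85. If all events occur on drug, the rate is understated by 1 − 85/113 = 24.8%. For an assumed stop at Day 29 with 28 days of follow-up, 57 days replace 29, an understatement of 49%. With equal off-drug hazards, an on-drug rate ratio of 2.0 becomes (2 × 85 + 28)/113 = 1.75, and 1.5 becomes 1.38. The planned exposure adjustment therefore does not separate the periods.

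**The case against.** The strongest reply is that the SAP has chosen a defensible window. AEs are recorded through the last visit. For a completer, 28 days after Day 85 is Day 113, so the SAP's window coincides with the protocol's own collection period. It catches delayed infections and laboratory recovery. Protocol 9.3 leaves detailed safety analyses to the SAP, and Protocol section 9 lets the SAP modify plans. All of this stands. It is a good reason to keep the through-follow-up table and no reason to demote it. It does not explain why that table should be the only one guaranteed.

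Three stronger readings are tempting, and the documents do not support them:

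- *The SAP departs from the protocol's AE endpoint.* The formal endpoint is treatment-emergent AEs, and the SAP repeats it. The on-treatment wording in Protocol 9.3 differs from the protocol's own endpoint list, so the inconsistency starts inside the protocol.
- *The protocol stops counting at Day 85 and the SAP at Day 113.* No end date is attached to on-treatment, so a Day 85 cut-off is an inference.
- *Every safety analysis is contaminated.* SAP Appendix 1 gives Weeks 13, 14 and 16 their own windows, so by-week safety displays show off-drug data apart.

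It is also fair that flares would fall mainly under the terms for worsening of atopic dermatitis. They would not spread into infection, haematology or gastrointestinal terms, and a reader could recognise that row for what it is.

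**Conclusion.** The point holds as a minor one, and acting on it is a cheap improvement. AE incidence and the tier 1 and tier 2 contrasts are guaranteed only with the off-drug follow-up pooled in, and neither AE term has a window.

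The expected distortion is small for most single preferred terms: 0.1 to 0.3 points at placebo rates of 5 to 10% with a hazard ratio of 2. It could be material for AD-worsening terms, but a reversal from −8.0 to +4.6 points needs the top of an assumed range (15% against 2% off drug). At 5% against 2% the difference is still −5.0. Since the direction is not fixed, a claim that the pooled tables overstate or understate harm would go beyond what the documents show. The exposure calculation contradicts its own definition whatever rates are assumed.

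**What to change.** - **SAP 5.2 and 7.4:** replace the permissive wording on the analysis without follow-up with a commitment that it will be done.
- **SAP 8.2.3:** require both the on-treatment and the through-follow-up AE and tier 1/2 tables. State the on-treatment window, relate it to the terms in Protocol 2.4.2.2 and 9.3, and tabulate AEs with onset in follow-up separately by arm. The through-follow-up table keeps its standing.
- **SAP 8.2.1:** for the on-treatment exposure-adjusted rates, compute exposure to last dose. Time to last visit can remain the denominator for the through-follow-up rates, labelled as observation time.

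The cost is SAP wording, one phase flag derived from AE onset and dosing dates, and one extra set of safety tables. No new data are needed, and delayed effects stay visible.
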